7.22.4 Relatedness of Adverse Events and Serious Adverse Events

Relationship of an AE or SAE to investigational product, device, device surgical procedure, or IT administration process is to be determined by the investigator based on the definitions in Table 7-4:

Table 7-4 Adverse Event Relatedness

Relationship to Product(s)	Definition
Not Related	Unrelated to study drug, device, device surgical procedure, or IT administration process.
Possibly Related	A clinical event or laboratory abnormality with a reasonable time sequence to administration of study drug, device, device surgical procedure, or IT administration process but which could also be explained by concurrent disease or other drugs or chemicals.

Table 7-4 Adverse Event Relatedness

Relationship to Product(s)	Definition
Probably Related	A clinical event or laboratory abnormality with a reasonable time sequence to administration of study drug, device, device surgical procedure, or IT administration process unlikely to be attributable to concurrent disease or other drugs and chemicals and which follows a clinically reasonable response on de-challenge. The association of the clinical event or laboratory abnormality must also have some biologic plausibility, at least on theoretical grounds.
Definitely Related	The event follows a reasonable temporal sequence from administration of the medication, device, device surgical procedure, or IT administration process follows a known or suspected response pattern to the medication, is confirmed by improvement upon stopping the medication (dechallenge) and reappears upon repeated exposure (rechallenge). Note that this is not to be construed as requiring re-exposure of the patient to study drug; however, the determination of definitely related can only be used when recurrence of event is observed.

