10.6 Efficacy, Safety, and Pharmacodynamic Evaluations

10.6.1 Primary Analyses

10.6.1.1 Safety Analysis

In general, safety assessments will be based on all assessments post-baseline. The assessment of safety will be based primarily on the frequency of AEs, and on the frequency of clinically notable abnormal vital sign and laboratory values. Changes from baseline will be calculated by subtracting the baseline value from the post-baseline value.

All enrolled patients who had an IDDD surgical procedure and/or received administration of HGT-1410 will be included in the safety analysis.

Adverse events will be recorded throughout the study and at early termination. Adverse events and medical conditions will be coded using the Medical Dictionary for Regulatory Activities (MedDRA).

Adverse events will be summarized by presenting, for each dose group, the number and percentage of patients having any AE, having an AE in system organ class, and having each individual AE. In addition, those events which resulted in death or were otherwise classified as serious will be presented in a separate listing. The incidence of treatment-emergent adverse events, defined as all AEs from the time of the surgery for IDDD implantation to the last follow up contact, ie, 30 days after the last HGT-1410 administration, (new or worsened from baseline) will be summarized by system organ class, severity, type of adverse event and relationship to trial medication/procedure.

Treatment-emergent AEs deemed related to HGT-1410 administration will be summarized separately.

IDDD and procedure-related AEs will be summarized within system organ class by preferred term. IDDD and procedure-related AEs will be tabulated by severity (mild, moderate, severe) and degree of relatedness. Separate tabulations will be provided for adverse events related to the IDDD, device surgical procedure (including post-implant infections) and IT administration process. These summaries will be presented by device and overall, as appropriate.

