7.22.1.4 IDDD-related Adverse Events

IDDD ADVERSE EVENTS

Examples of AEs related to use of the IDDD include, but are not limited to, the following: device failure, device malfunction, incorrect connection of IDDD components, erosion of the portal/catheter through the skin, fibrin sheath formation around the catheter tip, hematoma, implant rejection, migration of the portal/catheter, occlusion of the portal/catheter, portal site, or subcutaneous tract infection. The device may also need to be replaced or repaired as needed. A malfunction of the device (defined in Section 7.22.2.2) should not be entered as an AE unless it has physiological consequences. In the event of a device failure (defined in Section 7.22.2.3), the device may need to be replaced or repaired. Hospitalization for such a procedure will be reported as a serious adverse event (SAE). Details of the cause of IDDD malfunction or failure will be recorded on the Device Malfunction/Failure CRF. A list of the more common IDDD AEs is included in [Appendix 3](#).

DEVICE SURGICAL PROCEDURE-RELATED ADVERSE EVENTS

Examples of AEs related to device surgical procedures include, but are not limited to, the following: events that occur during or following IDDD implant/explant, IDDD adjustment, full revision, partial revision, IDDD removal, and delayed re-implantation after previous IDDD removal (such as complications of anesthesia, excessive bleeding, wound hematoma) and post operative complications (such as post-operative infection).

IT ADMINISTRATION PROCESS ADVERSE EVENTS

Intrathecal administration-process AEs include those caused by anesthesia during drug administration, drug administration issues (eg, extravasation during infusion or hematoma due to Huber needle) or complications of lumbar puncture.

RISKS ASSOCIATED WITH ANESTHESIA REQUIRED FOR STUDY ASSESSMENTS

The use of an IDDD has been chosen to minimize the risks inherent in utilizing novel delivery systems and to alleviate the need for multiple administrations of anesthesia required for drug injection via repeated LP. The risks from anesthesia include respiratory depression, aspiration, cardiac events, hypoxia, hypotension and hypertension, difficult intubations and extubations, stroke, rapid changes in body temperature, laryngospasm or laryngeal edema, allergic reaction, and death. Patients will be closely monitored for changes in vital signs and related events.

RISKS ASSOCIATED WITH LUMBAR PUNCTURE

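### Table 7-4 words its Definitely Related level for a drug, so a one-off surgical or device injury cannot be rated definitely related

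*Protocol*

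**What the plan says.** Section 7.22.4 sets one scale for four possible causes: "Relationship of an AE or SAE to investigational product, device, device surgical procedure, or IT administration process is to be determined by the investigator", using the definitions in Table 7-4. The wording of the table is the same in the Amendment 6 and Amendment 7 texts.

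- *Definitely Related* names all four causes in its timing clause. The event must then be one that "follows a known or suspected response pattern to the medication", and that "is confirmed by improvement upon stopping the medication (dechallenge) and reappears upon repeated exposure (rechallenge"). The note waives deliberate re-exposure to study drug, but still states that "the determination of definitely related can only be used when recurrence of event is observed".
- *Probably Related* asks for suitable timing, other causes being unlikely, biologic plausibility, and an event "which follows a clinically reasonable response on de-challenge". This row does not say that the medication is what must be withdrawn.
- *Possibly Related* asks for suitable timing, "but which could also be explained by concurrent disease or other drugs or chemicals".

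The visible text has no separate scale or exception for device, surgical or IT-process events. Section 7.22.1.4 nevertheless expects such events. Its list of surgical-procedure events ends with "delayed re-implantation after previous IDDD removal (such as complications of anesthesia, excessive bleeding, wound hematoma"). Section 10.6.1.1 says how they will be reported: "IDDD and procedure-related AEs will be tabulated by severity (mild, moderate, severe) and degree of relatedness", with separate tabulations for the device, the surgery and the IT process.

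**The concern.** A causality scale is useful only if its levels can be reached by the events it is meant to grade. Here the top level depends on withdrawing and re-meeting a drug, yet it is applied to operations, implants and punctures. A surgical complication with an obvious cause normally happens once, and stopping the medication says nothing about it.

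The device question matters in this study. The synopsis and Section 1.1 say that the first device had more complications than expected and that a second was brought in. Section 10.6.1.1 plans to present device and procedure events by device and overall. If the upper level is closed to one-off events by definition, an empty or sparse *definitely* column is a product of the wording and not a finding about the device or the surgery. With at most 12 patients, a few events placed one level lower would be visible in the table.

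**Working it through.** The protocol gives no figure to reproduce and no arithmetic applies. The check is to run the Table 7-4 criteria on the kinds of event the protocol itself anticipates.

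**Single wound hematoma at the implant incision (Section 7.22.1.4).**
- *Definitely*: timing is met. A response pattern to the medication does not apply. Improvement on stopping the medication is uninformative. Recurrence is not observed. The level is closed.
- *Probably*: timing, unlikely alternative causes and plausibility are met. A completed operation cannot be withdrawn, so the de-challenge clause either fails or must be read loosely.
- *Possibly*: timing is met, but the row describes an event with another plausible explanation, which is untrue of this one.
- *Not Related* is plainly wrong, so the event still ends in one of the three related levels, though never the top one.

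**Cerebrospinal fluid leak or catheter damage that resolves after the device is removed or revised.**
- *Definitely*: closed without recurrence. Even with recurrence, the clauses about the medication do not fit.
- *Probably*: removal or revision can reasonably serve as de-challenge, because this row does not name the medication. The level is open.

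**Headache after lumbar puncture.**
- Section 6.3.2 allows up to 12 consecutive punctures, so recurrence can be observed. The note's recurrence condition can be met, although the wording about stopping the medication still does not fit. This is not a good example of the problem.

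**Where the level is used.**
- Section 10.6.1.1 tabulates device and procedure events by degree of relatedness, so the split between levels matters there.
- Section 7.24 (stopping rule) counts possibly, probably and definitely alike. Moving an event among the three changes nothing.
- Section 7.22.5.2 records the source (device, device surgery, IT process) as a separate entry, with as many options marked as apply. Moving an event among the levels does not remove it from its source.

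The cleanest failing case is therefore the single surgical injury at *Definitely*. The bar at that level covers every non-recurring device, surgical and IT-process event. That is a consequence of the definition and not a count of events.

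**The case against.** The strongest reply is that little depends on the top level. The adverse-event endpoint in Section 3.1 is type and severity, not relatedness. Source is recorded separately, any-related totals are unchanged, and the stopping rule pools the three levels. Device harm is also captured without Table 7-4: causes of malfunction or failure go on their own form (Section 7.22.1.4), failures leading to scheduled surgical revision are reported as serious (Section 7.22.1.5), failure proportions, rates and times are summarised (Section 10.6.2.1), and the final cause of failure is reviewed (Section 11.8). All of this stands, and it limits the point.

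A reader might go further and infer that the table understates how much harm is attributed to the device and surgery, or that one-off events are shut out of *Probably* as well. The documents do not support either. A surgical hematoma is still counted as surgery-related; only its level shifts. For device events, removal or revision can be the de-challenge. For completed operations the *Probably* wording is awkward rather than an explicit bar like the recurrence note.

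One further caution stands. Sections 10.6.1.1, 10.6.2.1 and 11.8 can be read only in their Amendment 6 text. The Amendment 7 contents list keeps these headings, but the text is not shown.

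None of this answers the core defect: the scale claims to cover four causes, and its top level is worded for one.

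**Conclusion.** The point holds in a limited form. Under Table 7-4 as written, a single, non-recurring surgical, device or IT-process injury cannot be rated definitely related, whatever the evidence. For completed surgical events the *Probably* level is also hard to apply.

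The consequence is confined to how device and procedure events divide among possibly, probably and definitely in the Section 10.6.1.1 tabulation. Its numerical size cannot be stated, because the protocol gives no event counts. Source attribution, any-related counts, the stopping rule, device-failure summaries and the type-and-severity endpoint are not affected.

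The conclusion assumes that investigators apply the table literally, that no device-specific guidance exists outside the visible text, and that the Amendment 7 analysis section keeps the tabulation by degree. That sites will in fact rate differently from one another is possible but not shown.

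**What to change.** Split Table 7-4 by cause. Keep the dechallenge and rechallenge wording for study drug only. For device, device surgery and IT process:

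- *Probably Related*: suitable timing and a plausible mechanism, with other causes unlikely.
- *Definitely Related*: suitable timing and mechanism plus direct evidence, such as an imaging, operative or explant finding, with other causes excluded.
- Neither level should require medication dechallenge or recurrence.

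Apply the revised definitions to events from the amendment onward. Re-rating earlier events in an open-label study invites hindsight bias. If it is done, keep the original ratings and report both sets.

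The cost is a short amendment and eCRF completion guidance. More device and procedure events will appear in the upper relatedness levels, and tables that span the change will need a note on which definitions applied.

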7.22.5 Procedures for Recording and Reporting Adverse Events

7.22.5.1 Reporting Serious Adverse Events Related to Study Procedures

Any SAE regardless of relationship to investigational product, device, device surgical procedure, or IT administration process that occurs in a patient after informed consent (and assent if applicable) should be recorded by the clinical site on an SAE form that is to be transmitted to the Shire Medical Monitor and to the Shire Pharmacovigilance and Risk Management Department at the contact number provided below. The SAE must be completely described on the patient's eCRF, including the judgment of the investigator as to the relationship of the SAE to the investigational product and or device. The investigator will promptly supply all information identified and requested by the sponsor (and/or contract research organization [CRO]) regarding the SAE as to the relationship of the SAE to study drug, device, or procedure.

The investigator must report the SAE to the Shire Pharmacovigilance and Risk Management Department AND to the Shire Medical Monitor on an SAE form. The SAE form must be completed and FAXED or scanned and EMAILED (PDF sent by e-mail) within 24 hours of the investigator's learning of the event to:

Shire Pharmacovigilance and Risk Management Department:

International FAX: [REDACTED] **United Kingdom OR**

United States FAX: [REDACTED]

Email: [REDACTED]

AND

Shire HGT Medical Monitor:

FAX: [REDACTED] **(United States)**

The investigator may also call the medical monitor directly (optional):

Shire HGT Medical Monitor: [REDACTED] DO

[REDACTED]
Shire HGT

Work: [REDACTED]

Cell: [REDACTED] (24 hour access)

Email: [REDACTED]

AND

Clinical Project Manager CC'd: [REDACTED]

Any follow-up information must also be completed on an SAE form and faxed or scanned to the same numbers or e-mail address listed above.

In the event of a severe and unexpected, fatal, or life-threatening SAE, the clinical site must contact the Shire Medical Monitor by telephone; this is in addition to completing and transmitting the SAE form as stated above. The following provides contact information for the Shire Medical Monitor.

If an SAE is assessed as severe and unexpected, or life-threatening, contact:
--

[REDACTED] DO
[REDACTED]
Shire Human Genetic Therapies, Inc.
[name]
[name]
Telephone: [REDACTED]
Fax: [REDACTED] (United States)
Mobile: [REDACTED] (24-hour access)

The investigator must promptly report all required information to the Institutional Review Board (IRB)/Independent Ethics Committee (IEC). It is the responsibility of the sponsor to ensure that each investigator receives a copy of any CIOMS I/MedWatch report that has been submitted to the appropriate regulatory agencies notifying them of an unexpected related SAE. The investigator or sponsor must ensure that the IRB/IEC receives a copy of the report and that a copy is also filed within their study files. In addition, the sponsor will also notify the investigators and IRBs/IECs of all deaths that occur during the study, irrespective of relationship to study medication

7.22.5.2 Eliciting Adverse Events

Patients should be asked non-leading questions (eg, "How do you feel?") and further questions should be posed if there is indication of an AE. The questioning should be conducted with due

regard for objectivity and, in particular, the questioner should gather information regarding AEs from questioning the patient, the patient's parent/guardian, spontaneous report by the patient or parent/guardian, laboratory reports, and any health care provider's observations.

The onset date, resolution date, treatment administered, and outcome of each AE must be recorded on the appropriate eCRF. The relationship of each AE to study medication must be recorded. In addition AEs may be considered to be related to the IDDD, the IDDD surgical procedure, or the IT administration process. Since the AE may be deemed to be related to more than one of these factors, as many of these IDDD-related options as apply should be indicated on the eCRF.

7.22.5.3 Protocol Deviations for Medical Emergency or Adverse Event

During and following a patient's participation in the study, the investigator should ensure that adequate medical care is provided to a patient for any AEs, including clinically significant laboratory test results.

The investigator should inform the patient, the patient's parent(s), or the patient's legally authorized representative when medical care is needed for intercurrent illness(es) of which the investigator becomes aware. In an emergency situation, the investigator should contact the Shire Medical Monitor (see Section 7.22.5.1).

Only when an emergency occurs that requires an immediate deviation from the protocol for the safety of a patient, will there be such a deviation and this will be only for that patient.

The investigator or other physician in attendance in such an emergency must contact the Shire Medical Monitor as soon as possible.

The investigator, along with the Shire Medical Monitor, will make a decision as to whether or not the patient should continue in the study prior to the next scheduled dose. The departure from the protocol and the grounds for it should be stated in the eCRF.

7.23 Abuse, Overdose and Medication Errors

Abuse, misuse, overdose or medication error must be reported to the sponsor according to the SAE reporting procedure whether or not they result in an AE/SAE as described in Section 7.22.

- **Abuse** – Persistent or sporadic intentional intake of investigational medicinal product at a dose higher than prescribed per protocol (but below the dose defined for overdose) or when used for non-medical purpose (eg, altering one's state of consciousness)
 - **Misuse** – Intentional or unintentional use of investigational medicinal product other than as directed or indicated at any dose, which is at or below the dose defined for overdose (Note: This includes a situation where the test article is not used as directed at the dose prescribed **by the protocol**)
 - **Overdose** – Overdosage with adverse clinical consequences is not anticipated with the use of HGT-1410. Additionally, HGT-1410 will be given in a clinical setting by a health care provider.
-

- **Medication Error** – A mistake made in prescribing, dispensing, administration and/or use of the investigational medicinal product.

7.24 Safety-related Study Stopping Rules

If any patient experiences a life-threatening (Grade 4) adverse event or death which is considered by the sponsor to be possibly, probably, or definitely related to study drug **or the IDDD**, or if 2 or more patients experience a Grade 3 adverse event during the trial that is considered by the sponsor to be possibly, probably, or definitely related to the study drug **or the IDDD**, then the site will be instructed to halt further HGT-1410 administration to all patients and the safety data reviewed. Following a review of safety data, the study will be either:

- Resumed unchanged
- Resumed with modifications to the protocol or
- Terminated

Patient safety will be monitored on a continuous basis during this study until the last patient completes his or her last scheduled study visit/assessment.

7.25 Pregnancy

Pregnancy and breast feeding are exclusion criteria. Only female patients who have reached menarche will be tested for pregnancy in HGT-SAN-067. If applicable, this will occur at study start and before each dose of HGT-1410 throughout the study. Pregnancy testing will be performed on a blood or urine sample. Patients with a positive or inconclusive result will not be eligible for this study.

At study start, a pregnancy test will be performed if more than 30 days have passed since the initial screening sample. Throughout the study pregnancy testing will occur prior to each dose of HGT-1410. The clinical site's local laboratory will analyze and report all pregnancy testing results. If a pregnancy test is positive the patient will be discontinued from the study, and the investigator must contact the Shire Medical Monitor.

Pregnancy is not to be reported as an AE; the Pregnancy Reporting Form, found in the Study Operations Manual along with instructions for completion, should be used to report the pregnancy. The pregnancy will be followed up through delivery or final outcome.

7.26 Removal of Patients from the Trial or Study Drug

The patient's parent or legally authorized representative acting on behalf of the patient is free to withdraw consent and discontinue participation in the study at any time without prejudice to further treatment. Since this is an extension trial, there will be no replacement of patients who discontinue the study for any reason.

A patient's participation in the study may be discontinued at any time at the discretion of the investigator, sponsor, or medical monitor. The following may be justifiable reasons for the investigator, sponsor, or medical monitor to remove a patient from the study:

- Adverse Event: If a patient experiences an AE which, in the judgment of the investigator, the sponsor, or the medical monitor, presents an unacceptable consequence or risk to the patient.
- Adverse Laboratory Experience: If a patient has an adverse laboratory experience which, in the judgment of the investigator, the sponsor, or the medical monitor, presents an unacceptable consequence or risk to the patient, the patient may be withdrawn from the study.
- Comorbidity: If a patient develops comorbidity during the course of the study that is independent of the study indication, and treatment is required that is not consistent with protocol requirements.
- Intercurrent Illness: If a patient develops an illness during the course of the study that is not associated with the condition under study, and which requires treatment that is not consistent with protocol requirements.
- Refusal of Treatment: If the patient, the patient's parent(s) or legally authorized representative(s) discontinues participation in the study, or the patient is discontinued by the investigator, reasonable efforts will be made to follow the patient through the end of study assessments. The reason for refusal will be documented on the eCRF.
- Withdrawal of Informed Consent: A patient's parent or legally authorized representative may withdraw his informed consent to participate in the study at any time.
- Cerebrospinal fluid leukocyte count >100 cells per cubic millimeter for 2 consecutive months.
- New onset seizure.
- Anaphylactic reaction beyond reasonable management as described in the Investigator's Brochure.
- Clinically problematic intubations or extubations, which may preclude safe airway management and anesthesia.
- Development of refractory spinal fluid leakage.
- Clinically significant prolonged (eg, greater than 24 to 48 hours) worsening in mental status, including development of new focal or non-focal neurological symptoms, or recurrence of a previously stable prior medical problem judged due to study drug or participation that is exclusive of effects from anesthesia.
- Non-compliance, including failure to appear at 1 or more study visits.
- The patient was erroneously included in the study.
- The patient develops an exclusion criterion.
- The study is terminated by the sponsor.
- The patient becomes pregnant during the trial.

If a patient discontinues the study the Patient Completion/Discontinuation eCRF describing the reason for discontinuation must be completed. Any AE's experienced up to the point of discontinuation must be documented on the AE eCRF.

If AEs are present when the patient withdraws from the study, the patient will be re-evaluated within 30 days of withdrawal. All ongoing SAEs at the time of withdrawal will be followed until resolution.

At the time of discontinuation or withdrawal, patients will be asked to participate in all safety and efficacy evaluations required for the end of study visit and for the safety follow-up visit.

Participation in these EOS procedures will be strongly encouraged, but is voluntary for those patients electing to discontinue from the study. The patient will be scheduled for the removal of the IDDD.

